7.3 Total number of samples and blood withdrawn

During the study the following volume of blood will be collected:

for routine laboratories analysis:

Screening visit: 12.5 mL
Final visit/ETV: 12.5 mL

for coagulation:

Screening visit: 4.5 mL

for PK analysis:

Treatment T: 21 samples x 8 mL = 168 mL
Treatment R: 21 samples x 8 mL = 168 mL

In total 365.5 mL of blood (not exceeding a normal blood donation) will be withdrawn from each subject.

8 ASSIGNMENT OF STUDY TREATMENT

8.1 Randomization

The randomization list will be computer-generated by the Biometry Unit of the contract research organization (CRO), using the PLAN procedure of SAS® version 9.3 (TS1M1) (12) or higher (the actual version will be stated in the final CSR). The randomization list will be supplied to the study site before study start and will be attached to the final CSR.

Randomization will be stratified by sex in order to have the same number of men and women for every sequence of treatments.

8.2 Treatment allocation

Subjects will be assigned to one sequence of treatments (e.g. TR or RT) i.e. to receive the IMP in fed conditions (T treatment) during period 1 and in fasting conditions (R treatment) in period 2 or vice versa according to their randomization number.

Randomization number will be given to the subjects on study Day -1 of period 1 and will be used to assign the treatment sequence.

8.3 Blinding

This is an open-label trial. No masking procedure will be applied since an open-label design was considered adequate for evaluating objective measures such as pharmacokinetic parameters. All the personnel involved in the analytical determinations of ladarixin and its metabolites in plasma samples collected from the volunteers will be maintained in blind conditions.

9 EVALUATION PARAMETERS

9.1 Study variables

9.1.1 Primary variables

C_{max} and AUC_{0-t} of plasma DF 2156Y after single dose administration of 400 mg of ladarixin under fed and fasting conditions

9.1.2 Secondary variables

- $AUC_{0-\infty}$, t_{max} , $t_{1/2}$, λ_z and F_{rel} of plasma DF 2156Y after single dose administration of 400 mg of ladarixin under fed and fasting conditions
- C_{max} , AUC_{0-t} , $AUC_{0-\infty}$, t_{max} , $t_{1/2}$, λ_z and F_{rel} of plasma DF 2156Y and its metabolites (DF 2108Y and DF 2227Y) after single dose of 400 mg of ladarixin under fed and fasting conditions measured and calculated in healthy men and healthy women
- Treatment-emergent adverse events (TEAEs), vital signs (BP, PR, BT), body weight, ECGs, physical examinations, laboratory parameters (hematology, blood chemistry and urine analysis)

9.2 Pharmacokinetic assessments

9.2.1 Pharmacokinetic parameters

The following PK parameters will be measured and/or calculated for DF 2156Y and its metabolites, DF 2108Y and DF 2227Y, using the validated software Phoenix WinNonlin® version 6.3 (13) or higher (actual version will be stated in the final report):

C_{max} : Maximum plasma concentration

t_{max} : Time to achieve C_{max}

λ_z : Terminal rate constant, calculated, if feasible, by log-linear regression using at least 3 points

$t_{1/2}$: Half-life, calculated, if feasible, as $\ln 2/\lambda_z$

AUC_{0-t} : Area under the concentration-time curve from administration to the last observed concentration time t , calculated with the linear trapezoidal method

$AUC_{0-\infty}$: Area under the concentration-time curve extrapolated to infinity, calculated, if feasible, as $AUC_{0-t} + C_t/\lambda_z$, where C_t is the last measurable drug concentration

$\%AUC_{extra}$: Percentage of the residual area (C_t/λ_z) extrapolated to infinity in relation to the total $AUC_{0-\infty}$, calculated, if feasible, as $100 \times [(C_t/\lambda_z)/AUC_{0-\infty}]$

F_{rel} : Relative bioavailability, calculated as ratio $AUC_{0-t}(T)/ AUC_{0-t}(R)$

The sampling schedule is considered adequate if the ratio $AUC_{0-t}/AUC_{0-\infty}$ equals or exceeds a factor of 0.8 (i.e. if $\%AUC_{\text{extra}}$ is <20%) for more than 80% of the individual PK profiles. This assures that the primary variable AUC_{0-t} covers a sufficient percentage of the theoretical total extent of exposure.

The quality of log-linear regression (and, consequently, the reliability of the extrapolated PK parameters) should be demonstrated by a determination coefficient $R^2 > 0.8$. Individual extrapolated parameters, when considered unreliable, will be reported as NC (not calculated).

9.3 Safety assessments

Safety and general tolerability of the IMP will be based on TEAEs, physical examinations including body weight, vital signs, routine hematology, blood chemistry, urinalysis laboratory tests and ECGs.

10 STATISTICAL METHODS

The data documented in this study and the parameters measured will be evaluated and compared using classic descriptive statistics, i.e. geometric mean (PK data only), arithmetic mean, standard deviation (SD), coefficient of variation (CV) %, minimum, median and maximum values for quantitative variables, and frequencies for qualitative variables.

Not available data will be evaluated as “missing values”. The statistical analysis of demographic and safety data will be performed using SAS® version 9.3 (TS1M1) (12) or higher (the actual version will be stated in the final report).

The statistical analysis of PK parameters will be performed using Phoenix WinNonlin® version 6.3 (13) or higher and SAS® version 9.3 (TS1M1) or higher.

10.1 Analysis Sets

10.1.1 *Definitions*

A subject will be defined as screened after the signature of the informed consent, regardless of the completion of all the screening procedures.

A subject will be defined as eligible if he/she meets all the inclusion/exclusion criteria. Otherwise he/she will be defined as a screen failure.

A subject will be defined as enrolled in the study if he/she is included into the interventional phase of the study. The enrolment will be performed through randomized allocation to one treatment sequence.

An eligible but not enrolled subject will be defined as a reserve.

A subject will be defined as randomized in the study when he/she is assigned to one randomized treatment sequence.

In the present study, randomized subjects will be the same as enrolled subjects.

- Enrolled set: all enrolled subjects. This analysis set will be used for demographic, baseline and background characteristics
- Safety set: all subjects who receive at least one dose of study treatments. This analysis set will be used for the safety and tolerability analyses
- PK set 1: all subjects randomized who fulfill the study protocol requirements in terms of investigational treatment intake and have evaluable PK data readouts for DF 2156Y with no major deviations that may affect the PK results. This analysis set will be used for the statistical analysis of the PK results for DF 2156Y.
- PK set 2: all subjects randomized who fulfill the study protocol requirements in terms of investigational treatment intake and have evaluable PK data readouts for DF 2108Y and DF 2227Y, with no major deviations that may affect the PK results. This analysis set will be used for the statistical analysis of the PK results for DF 2108Y and DF 2227Y.

Each subject will be coded by the CRO Biometry Unit as valid or not valid for the safety set and the PK sets. Subjects will be evaluated according to the treatment they actually receive.

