Plasma samples were collected at pre-dose and 1, 2, 3, 4, 5, 6, 7, 8, 9, 10, 12, 16, 24, 36, 48, 60, 72, 84, 96, 120, 144 and 168 h post-dose. Urine samples were collected in the following time periods: 0-12, 12-24, 24-36, 36-48, and during subsequent intervals of 24 up to 168 h post-dose. Faces samples were collected in the intervals 0-24, 24-48, 48-72 and 72-96 h post-dose.

Main PK parameters of ladarixin and its metabolites measured and calculated after single dose of 400 mg of ladarixin are presented in the following table.

Table 1.4.2.1 PK parameters of ladarixin and its metabolites measured and calculated after single dose of 400 mg of ladarixin to healthy men (N=6)

Variable (Unit)	DF 2156Y (N=6)	DF 2108Y (N=6)	DF 2227Y (N=6)
C _{max} (µg/mL)	54.86±7.41	0.938±0.104	0.692±0.116
t _{max} (h)	1.75±1.12	14.92±772	45.98±15.91
AUC _{0-t} (µg/mL·h)	912.40±155.62	49.58±10.07	51.93±9.40
AUC _{0-∞} (µg/mL·h)	921.54±159.99	50.36±10.61	NC
t _{1/2} (h)	13.62±2.66	18.32±2.65	NC
V _z /F (L)	8.19±1.84	ND	ND
Cl/F (L/h)	0.42±0.07	ND	ND
Ae _{0-t} (% of dose)	79.67±9.99	2.00±0.45	1.08±0.33
Cl _R (L/h)	0.34±0.05	0.131±0.03	0.068±0.023
Ae _{Feces0-t} (µg)	120.76±52.31	0.0	0.0

mean±SD are reported; NC: not calculated; ND: not determined

1.4.3 Phase I safety, tolerability and bioavailability single and multiple dose study in healthy men

Twenty-four (24) men were randomized into 2 cohorts including 12 subjects (9 subjects received ladarixin and 3 subjects received placebo). Ladarixin was administered at the dose of 300 and 400 mg for 7 days. The subjects received a single dose on days 1 and 8 and twice daily every 12 h on days 3 to 7. Plasma samples were collected as follows:

Day 1: pre-dose and 0.5, 1, 1.5, 2, 3, 4, 5, 6, 8, 10, 12, 24 h post dosing

Day 3: Day 4, Day 5, Day 6: before the first and the second daily dosing

Day 7: before and 1h after the first and the second daily dose

Day 8: pre-dose and 0.5, 1, 1.5, 2, 3, 4, 5, 6, 8, 10, 12, 24, 36, 48, 60 and 72 h post dosing

Main PK parameters of ladarixin and its metabolites measured and calculated after single dose of 400 mg of ladarixin are presented in the following table.

Table 1.4.3.1 PK parameters of ladarixin and its metabolites measured and calculated after single dose of 400 mg of ladarixin to healthy men (N=9)

Variable (Unit)	DF 2156Y (N=9)	DF 2108Y (N=9)	DF 2227Y (N=9)
C_{\max} (µg/mL)	81.10±13.99	0.82±0.19	0.40±0.08
t_{\max} (h)	0.52 (0.50 – 1.52)	10 (8 – 12)	8.02 (5.02 – 12)

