7.2 Sampling for pharmacokinetic analysis

7.2.1 *Venous blood sampling*

Venous blood samples (8 mL) will be collected from a forearm vein at the following times:

- pre-dose (0), 0.25, 0.5, 1, 1.5, 2, 3, 4, 5, 6, 8, 10, 12, 18, 24, 30, 36, 48, 54, 60 and 72 h post-dose

Actual sampling times for each subject will be recorded in the individual electronic case report forms (eCRF). The actual sampling times should not exceed the recommended tolerance ranges presented in the table below. Any deviation outside the recommended ranges will be verified through Data Clarification Forms and, if confirmed, will be reported as protocol deviation, although it will not automatically lead to the exclusion of the concerned subjects from the PK Set.

Table 7.2.1.1 Tolerance ranges for the scheduled sampling times

Sampling time	Tolerance range
Pre-dose (0)	Within 40 min before IMP administration
0.25 h (15 min)	0 min
0.5 h (30 min)	± 1 min
1, 1.5 h	± 3 min
2, 3, 4, 5 h	± 5 min
6, 8, 10, 12, 18, 24, 30 h	± 10 min
36, 48, 54, 60, 72 h	± 30 min

Blood samples for PK analysis will be collected using an indwelling catheter with switch valve. The cannula will be rinsed, after each sampling, with about 1 mL of sterile saline solution containing 20 I.U./mL Na-heparin. The first 2 mL of blood will be discarded at each collection time to avoid contamination of the sample with heparin.

The remaining 6 mL will be collected from the catheter and transferred with a syringe into heparinized tubes (Li-heparin).

The samples will be stored on ice for a maximum of 15 min. Then the samples will be centrifuged at 4° C for 10 min at 2500 g to obtain plasma. Each plasma sample will be immediately divided into 3 aliquots, P1 (500 µL), P2 (500 µL) and P3 (the remaining amount), in pre-labeled polypropylene tubes, and stored frozen at ≤-20° C until shipment to the analytical laboratory.

If any clinical assessment, such as vital signs measurement or ECG recording, is foreseen at the same time-point as blood sampling for PK analysis, blood collection will be performed at the scheduled time. However, vital signs and ECG parameters can be influenced by the blood sampling. Therefore, these assessments can be performed within 30 min before the pre-dose

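### PK set 2 requires evaluable data for both metabolites, so a failure specific to DF 2227Y would also remove usable DF 2108Y data; the expected loss is probably small

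*Protocol*

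**What the plan says.** Section 10.1.1 of the protocol defines two PK sets. PK set 1 is specific to the parent: its subjects must "have evaluable PK data readouts for DF 2156Y with no major deviations that may affect the PK results". PK set 2 is joint for the two metabolites: its subjects must "have evaluable PK data readouts for DF 2108Y and DF 2227Y, with no major deviations that may affect the PK results". The use of PK set 2 is then fixed: "This analysis set will be used for the statistical analysis of the PK results for DF 2108Y and DF 2227Y". No other set is named for either metabolite. Validity is assigned by subject and set, not by analyte: "Each subject will be coded by the CRO Biometry Unit as valid or not valid for the safety set and the PK sets".

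The word evaluable is not defined. Section 10.1.2 lists exclusion reasons that apply before bioanalysis (vomiting or diarrhoea, interfering medication, adverse events, administration errors, other events). Sections 9.2.1 and 10.4.1 handle unreliable extrapolated parameters by reporting them as NC. Section 10.4.2 lists Cmax, AUC0-t and AUC0-∞ of each analyte for the gender ANOVA.

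**The concern.** The condition ties one analyte's data to another's. A subject with a sound DF 2108Y profile but a DF 2227Y profile that cannot be evaluated is not valid for PK set 2, and so has no set in which the DF 2108Y data can be analysed.

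The condition serves no stated purpose. Section 10.4.2 names no joint model of the two metabolites and no metabolite ratio that would need the same subjects. What is at stake is the secondary comparison of DF 2108Y between men and women, with 18 of each planned, in the first study to evaluate the drug's pharmacokinetics in women (section 1.5).

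**Working it through.** The protocol gives no loss rate, power or precision figure for the metabolite analyses, so there is no figure to reproduce. The check asks what the rule does, which events could trigger it, and how much a loss would cost.

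**1. Events that could trigger the rule**
- *Late or incomplete DF 2227Y profile.* Under section 9.2.1, Cmax is the highest concentration and AUC0-t runs to the last observed concentration. Both exist even if the profile is still rising at 72 h. λz is "calculated, if feasible, by log-linear regression using at least 3 points", and if that fails only the extrapolated parameters become NC. No written rule removes the subject.
- *Missing samples.* Both metabolites are measured in plasma from the same draws (sections 7.2.1 and 7.2.2), so a missed draw affects both.
- *Section 10.1.2 events.* These are subject-level and affect every analyte.
- *Analyte-specific assay failure, or a DF 2227Y profile judged not evaluable.* This is the route by which the joint rule alone removes sound DF 2108Y data.

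**2. DF 2108Y coverage with the last samples at "36, 48, 54, 60 and 72 h post-dose"**

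Inputs from Table 1.4.2.1 (400 mg, N=6, sampling to 168 h): Cmax 0.938 µg/mL, mean t_max 14.92 h, t1/2 18.32 h (λz = ln 2/18.32 = 0.0378 per h), AUC0-∞ 50.36 µg/mL·h. The SD printed for this t_max is not used. Share of AUC beyond 72 h:
- (a) Mono-exponential decline from mean t_max: C72 = 0.938 × 2^(−(72−14.92)/18.32) = 0.108 µg/mL; 0.108/λz = 2.86; 2.86/50.36 = 5.7%.
- (b) Formation and elimination model with formation half-life equal to the parent's 13.62 h (k = 0.0509): (e^(−72λz)/λz − e^(−72k)/k)/(1/λz − 1/k) = (1.734 − 0.503)/(26.43 − 19.65) = 18.1%.
- (c) Same model with k = 0.108, chosen to match t_max 14.92 h: 10.1%.
- (d) Across studies, with AUC0-48 of 32.46 from Table 1.4.3.1: (50.36 − 32.46) × 2^(−24/18.32)/50.36 = 14.3%.

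Coverage is therefore about 82–94% on mean values. It meets the section 9.2.1 ratio of 0.8, which the protocol wants "for more than 80% of the individual PK profiles". With t1/2 one SD longer (20.97 h), the tails under (a), (b) and (c) are 8.5%, 21.7% and 12.8%, so the margin is limited.

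**3. DF 2227Y coverage**
- Table 1.4.2.1 gives the t_max values for DF 2108Y and DF 2227Y as "14.92±772 45.98±15.91", with DF 2227Y t1/2 and AUC0-∞ NC. Assuming t_max is normal with mean 45.98 h and SD 15.91 h, P(t_max > 72 h) = P(Z > 1.64) = 5%.
- A peak nearer 54 h than 48 h (t_max > 51 h) leaves fewer than three scheduled samples after it: P(Z > 0.32) = 38%.
- Across studies, AUC0-72 is at most 19.60 + 24 × 0.692 = 36.2, or 70% of the 51.93 measured in the 168-h study.
- Table 1.4.3.1 (400 mg, N=9) gives DF 2227Y t_max as 8.02 h (5.02–12), against 45.98 h. That row does not close: a Cmax of 0.40 held for 48 h gives 0.40 × 48 = 19.2, below its AUC0-48 of 19.60. Neither value can be taken as settled.

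The 5% and 38% describe how often a peak is late or λz is not estimable. By step 1, neither is a rate of exclusion from PK set 2.

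**4. Cost of an assumed loss**
- *Sex difference.* With equal numbers per sex, the standard error is proportional to √(2/n per sex). For 18 per sex this is 0.333; for 17, 0.343 (+3%); for 16, 0.354 (+6%); for 14, 0.378 (+13%).
- *Fed/fasting contrast.* The 90% CI factor is exp[t(0.95, n−2) × s_w × √(2/n)]. At an assumed within-subject CV of 20% it is 1.082 for n = 36, 1.088 for n = 32 and 1.094 for n = 28.

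The protocol gives neither the losses nor the CV.

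**The case against.** The strongest reply is that the protocol's own rules prevent most of the harm. Late DF 2227Y kinetics lead to an NC for single parameters and not to exclusion, and shared draws mean that missing samples are not specific to one metabolite. Reserve aliquots (section 7.2.3.2) make a lasting assay failure unlikely, and DF 2227Y peaks are 8 to 14 times the earlier quantification limit (0.40/0.05 and 0.692/0.05). The meaning of evaluable may be set in an SAP that is not shown, and a common set lets both metabolites be described on the same people. All of this stands as a limit on size. It does not remove the point, because the joint condition is a rule the protocol states and an SAP that follows it inherits it.

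A reader might infer that a large share of the 36 subjects would leave the DF 2108Y analysis. That requires evaluable to mean that extrapolated parameters exist. Nothing in the protocol says so, and it could leave PK set 2 nearly empty, since those parameters were NC for DF 2227Y even with sampling to 168 h.

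A reader might also infer a sharp contrast between a well-covered and a poorly covered metabolite. The evidence is less one-sided: DF 2108Y t1/2 and AUC0-∞ were also NC in the second 400 mg study, its projected 72-h concentration of 0.108 µg/mL is close to the earlier limit of 0.1, and the two studies disagree on DF 2227Y t_max.

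**Conclusion.** The point holds as a minor one. The definition can discard sound DF 2108Y data for reasons confined to DF 2227Y, and the protocol states no purpose for it. The expected loss is unknown and probably small. That judgement assumes that evaluable means measurable concentrations giving Cmax and AUC0-t. Only the metabolite analyses are affected, and the gender comparison is described as exploratory in a study sized without calculation. The primary DF 2156Y analysis uses PK set 1.

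It is also tempting to conclude that the loss would be related to sex and so bias the gender comparison. The documents do not support this: both earlier 400 mg tables come from men only, and nothing links DF 2227Y evaluability to sex.

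**What to change.** Replace PK set 2 with two sets that share the same treatment-intake and major-deviation conditions: PK set 2a, evaluable data for DF 2108Y, used only for DF 2108Y; and PK set 2b, evaluable data for DF 2227Y, used only for DF 2227Y. Equivalently, keep one set name and code validity by metabolite. Keep the rule that sets single unreliable extrapolated parameters to NC.

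The cost is one definition and one extra flag. The two metabolites may be reported on slightly different numbers of subjects, so each table should show its own n. Trial conduct does not change, so the end of the clinical phase, recorded in the note to file of 19 January 2021, is no obstacle in itself. The change should be documented before subjects are coded for the PK sets.

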10.1.2 Reasons for exclusion from the PK sets

Reasons for the exclusion of subjects from the PK sets before the bioanalysis are the following:

- vomiting and diarrhea before or after drug intake which could render the plasma concentration-time profile unreliable
- intake of concomitant medications which could render the plasma concentration-time profile unreliable
- AEs which could render the plasma concentration-time profile unreliable
- administration errors which could render the plasma concentration-time profile unreliable
- other events which could render the plasma concentration-time profile unreliable

If one of these events occurs, it will be noted in the eCRF as the study is being conducted.

10.2 Sample size and power considerations

The sample size was not calculated through any statistical calculation. A sample size of 36 subjects (18 men and 18 women) was estimated as sufficient for the descriptive purposes of the present study in compliance with the relevant EMA guideline for PK studies (8).

Drop-out subjects will not be replaced.

10.3 Demographic, baseline and background characteristics

10.3.1 Demography

Demographic characteristics will be listed and examined according to qualitative or quantitative data. Qualitative data will be summarized in contingency tables. Quantitative data will be summarized using classic descriptive statistics.

10.4 Analysis of pharmacokinetic parameters

10.4.1 Descriptive pharmacokinetics

A descriptive PK will be presented for plasma total and unbound DF 2156Y and its metabolites DF 2108Y and DF 2227Y. The results will be displayed and summarized in tables and figures. Individual and mean curves (+SD at sampling times), indicating inter-subject variability, will be plotted. Mean curves will be presented by treatment and by treatment and sex.

PK parameters of total plasma DF 2156Y and its metabolites DF 2108Y and DF 2227Y will be summarized by treatment and by treatment and sex.

Data below the lower quantification limit (BLQL) will be considered as 0 in the calculations and presented as BLQL in listings and tables. As a consequence of BLQL (i.e. 0) values, calculated geometric means (if requested) could be null. For this reason, in the presence of any null value, the geometric mean will be reported as NC. If for an individual PK curve, a log-linear regression with a correlation coefficient $R^2 > 0.8$ cannot be obtained, the extrapolated PK parameters will be reported as NC and considered missing in the calculations of descriptive statistics.

10.4.2 *Statistical comparison of pharmacokinetic parameters*

For the primary end-point evaluation of food effect, C_{max} , AUC_{0-t} and $AUC_{0-\infty}$ of total plasma DF 2156Y will be compared between fed and fasting conditions (T vs. R) using analysis of variance (ANOVA) for a cross-over design on log-transformed data for evaluation of the food effect. Period, treatment, sequence and subject within sequence will be taken in account as sources of variation and they will be treated as fixed effect.

The 90% confidence intervals (CI) will be calculated for the point estimates (PE, i.e. the T/R ratio of least square geometric means) of the PK parameters.

Established criteria for the absence of a food effect are that the 90% CI for the T/R ratio of the geometric means of the PK parameters under consideration are within the 80.00-125.00% range.

For the purpose of exploring the gender effect on bioavailability of ladarixin and its metabolites, following logarithmic transformation, C_{max} , AUC_{0-t} and $AUC_{0-\infty}$ of total plasma DF 2156Y and of DF 2108Y and DF 2227Y will be analyzed using ANOVA including sequence, period, treatment, subject within sequence, sex and sex*treatment interaction as fixed effect.

10.5 *Safety and tolerability evaluation*

➤ AEs

AEs will be coded by System Organ Class (SOC) and Preferred Term (PT), using the Medical Dictionary for Regulatory Activities (MedDRA).

AEs will be classified as pre-treatment AEs (PTAEs) and TEAEs, according to the period of occurrence, as follows:

- PTAEs: all AEs occurring after informed consent signature by the enrolled subject but before the first dose of IMP and not negatively affected by the first dose of IMP;
- TEAEs: all AEs occurring or worsening after the administration of the first dose of IMP.

Individual PTAEs and TEAEs will be listed in subject data listings. No summary table will be provided for PTAEs. TEAEs will be summarized by treatment and overall. The number and percentage of subjects with any TEAE and the number of TEAEs will be tabulated by SOC and PT, seriousness, relationship to treatment and severity.

➤ Physical examination

Date of the physical examination, overall investigator's interpretation (as normal or abnormal and, if abnormal, clinically significant or not clinically significant) and clinically significant abnormalities (if any) will be listed.

➤ Laboratory data

Date/time of samples collection, overall investigator's interpretation (as normal or abnormal and, if abnormal, clinically significant or not clinically significant) and all abnormalities found (if any) will be listed. All laboratory results will be listed and a table of all the abnormal values will be presented. The overall investigator's interpretation will be summarized using tables of frequency.

➤ Vital signs

Vital signs values will be listed and summarized by descriptive statistics.

➤ Body weight

Body weight values will be listed and summarized by descriptive statistics.

➤ ECG

Date/time of ECG recording, overall investigator's interpretation (as normal or abnormal and, if abnormal, clinically significant or not clinically significant) and all abnormalities found (if any) will be listed. The overall investigator's interpretation will be summarized using tables of frequency

11 DEFINITION AND HANDLING OF AEs AND SAEs

